11.7. Caregiver Global Impression-Severity Scale (CaGI-S)

The CaGI-S is a caregiver-rated scale that will be used to measure both the severity of the subject’s overall clinical condition and their apathy symptoms specifically.

To perform this assessment, the caregiver will answer the questions related to the severity of the subject’s overall dementing illness (cognition, behavior, and function) and apathy symptoms specifically based upon their observations over the past 4 weeks.

Scores are on a 7-point scale where 1 is “normal, no symptoms of apathy/normal, not at all impaired” and 7 is “extremely severe apathy/extremely severely ill”.

The questionnaire and the scores will be provided by WCG VeraSci.

Descriptive statistics of the CaGI-S scores will be presented by visit and change from Baseline to Visit 5 (Week 6) and Visit 6 (Week 12) in CaGI-S scores will be analyzed through an MMRM for the mITT as described in [Section 11](#). Additionally, all CaGI-S related individual data will be listed for the randomized patients with indicator for inclusion in the mITT analysis set.

11.8. Caregiver Global Impression-Change Scale (CaGI-C)

The CaGI-C is a caregiver-rated scale that will be used to measure change in both the subject’s overall dementing illness (cognition, behavior, and function) and their apathy symptoms specifically compared with before initiation of treatment with IMP. It is important to note that the caregiver will provide their assessment of the subject’s current condition compared with their condition at Baseline (Visit 2).

To perform this assessment, the caregiver will rate the subject’s change from baseline in their overall dementing illness (cognition, behavior, and function) and in their apathy symptoms specifically.

Scores are on a 7-point scale where 1 is “marked improvement in apathy/overall dementia” and 7 is “marked worsening in apathy/overall dementia”.

The questionnaire and the scores will be provided by WCG VeraSci.

Descriptive statistics of the CaGI-C scores will be presented by visit. Additionally, all CaGI-C related individual data will be listed.

12. INTERIM ANALYSIS

No interim analyses are planned in this study.

13. SUPPLEMENTARY ANALYSES

13.1. Adverse Events (Safety) By Treatment Period

The TEAE incidence will be summarized by two periods: Period 1 (Day 1 through Day 21; Step 1-4) and Period 2 (Day 22 through end of treatment) as well as TEAE incidence by actual dose level (0.25 mg, 0.5 mg, 1 mg, 2 mg, and 3 mg). The summary will be tabulated by SOC in internationally agreed order and PT in descending order of the higher dose group within SOC. Summary will also include a total column.

In addition, the incidence of TEAE leading to permanent discontinuation of treatment will be summarized by two periods: Period 1 (Day 1 through Day 21; Step 1-4) and Period 2 (Day 22 through end of treatment). The summary will be tabulated by SOC in internationally agreed order and PT in descending order of the higher dose group. Summary will also include a total column.

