On Day 22 (Visit 4), all subjects will take the Step 5 dose of IMP at the clinic. Subjects will be monitored for tolerability while undergoing concurrent assessments; after completion of all visit procedures, the investigator will assess whether the participant will continue with the new dose. Subjects who are unable to tolerate the dose at Step 5 may go back to the dose at Step 4 and continue on that dose for the remainder of the trial. Subjects who are able to tolerate the Step 5 dose will continue on this dose for the remainder of the trial and no further dosing adjustments are allowed.

[figure not shown]
Lack of tolerability should be of sufficient severity that it results in significant dysfunction or distress to the subject (eg, Common Terminology Criteria for Adverse Events [CTCAE] Grade 2/3). The medical monitor should be contacted in any instance

where the investigator is uncertain whether the subject is able to tolerate the stepwise dose increase.

No deviations in the dosing schedule, other than those noted above, are allowed.

The titration scheme, including the dosing decision time points, is presented in [Figure 2](#).

Figure 2 Dosing Schematic

Abbreviations: PBO = placebo.

Note: If “Yes” then continue with new dose; if “No” then stay at previous dose.

Assessments will be conducted at the Week 1, 3, 6, and 12 visits. Subjects will be instructed to take their dose of IMP at the clinic on days when visits occur. Blood samples for PK analysis will be collected at the Week 1, 3, 6, and 12 visits.

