6.4 Trial Treatment Compliance

Responsible trial personnel will dispense the IMP. The time and dose of each IMP administration, along with information on any missed or inappropriately administered dose, will be recorded in source documents and the electronic case report form (eCRF).

The guidance and intent of this trial is for caregivers to administer IMP. Therefore, subjects and caregivers must be counseled on the importance of taking the IMP as directed. If poor compliance is encountered (eg, multiple missed doses resulting in less than 80% overall compliance at any point in the trial), discontinuation of the subject from the trial should be considered. Subjects who habitually miss visits or habitually attend visits outside of the protocol-defined visit window are also defined as noncompliant and should be considered for discontinuation. The medical monitor should be contacted if the investigator is uncertain whether a subject's lack of compliance merits discontinuation from the trial.

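### SAP 13.1 splits adverse events at a fixed Day 21/22 and labels the first part Steps 1-4, but Step 5 can start on any of Days 19-25, so up to 3 days per subject can fall in the wrong period

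*SAP*

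**What the plan says.** SAP 13.1 (Adverse Events by Treatment Period) reports TEAE incidence by "two periods: Period 1 (Day 1 through Day 21; Step 1-4) and Period 2 (Day 22 through end of treatment". The same sentence adds a second summary, "as well as TEAE incidence by actual dose level (0.25 mg, 0.5 mg, 1 mg, 2 mg, and 3 mg". The next paragraph says that "the incidence of TEAE leading to permanent discontinuation of treatment will be summarized by two periods", with the same two periods and no dose-level split. Safety Day 1 is the date of the first dose (SAP 4.4.6).

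Protocol 4.1.2 ties the start of Step 5 to a clinic visit: "On Day 22 (Visit 4), all subjects will take the Step 5 dose of IMP at the clinic". It also says: "No deviations in the dosing schedule, other than those noted above, are allowed".

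In Protocol Table 1 and SAP Table 4 the window row shows ±3 days beginning at Visit 3. The next entry, ±5 days, begins at the Day 29 contact. Read by column position, Visit 4 has a ±3-day window. Study drug is dispensed at that visit.

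Protocol 9.4.4 also plans TEAE summaries by dose at the time of onset.

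**The concern.** The period boundary is a study day, while the event that it stands for, the first Step 5 dose, happens at a visit that is allowed to move. Nothing in SAP 13.1 links the two. For a subject seen early, the first days at Step 5 carry a heading that says Steps 1-4. For a subject seen late, the last days at Step 4 fall in Period 2.

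Safety and tolerability is the primary objective. Protocol 2.2.4 reports nausea as the most frequent adverse event in both earlier trials, and Protocol 4.3 gives nausea and vomiting as the reason for slow titration. If reactions to a dose increase cluster in the days just after it (an assumption, though a natural one), they are the events that a shifted boundary misplaces. TEAEs leading to discontinuation are also adverse events of special interest (Protocol 8.4.6.7). At the planned 25 subjects per arm, moving one subject between periods changes an incidence by 1/25 = 4 percentage points. Enrolment closed short of plan, so the change would be larger in a smaller arm.

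**Working it through.** **Inputs.** Step lengths are from SAP Table 2: 3, 4, 9, 5 and 63 days. The period boundary is from SAP 13.1. Nominal Visit 4 is Day 22 (Protocol 4.1.2). The ±3-day window is read by column position from Protocol Table 1 and SAP Table 4. I take events to be assigned by onset date, which SAP 13.1 does not state.

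**1. Reproduce the nominal boundary.** Steps 1-4 last 3 + 4 + 9 + 5 = 21 days, and the whole schedule lasts 21 + 63 = 84 days. The Day 21/22 cut is therefore exact when Visit 4 is on Day 22, except for an event on Day 22 before the clinic dose, which goes to Period 2.

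**2. Move Visit 4 across its window, 22 − 3 = 19 to 22 + 3 = 25.** For Visit 4 on day v, Step 5 days counted in Period 1 = max(0, 22 − v), and Step 4 days counted in Period 2 = max(0, v − 22).

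| Visit 4 day | Step 5 days in Period 1 | Step 4 days in Period 2 |
|---|---|---|
| 19 | 3 | 0 |
| 20 | 2 | 0 |
| 21 | 1 | 0 |
| 22 | 0 | 0 |
| 23 | 0 | 1 |
| 24 | 0 | 2 |
| 25 | 0 | 3 |

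The maximum is 3 days per subject: 3/21 = 14.3% of Period 1, or 3/63 = 4.8% of the nominal length of Step 5.

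**3. Where the dose also differs.** From Step 4 to Step 5 the 1.0 mg arm stays at 1.0 mg, placebo stays placebo, and the 3.0 mg arm goes from 2.0 to 3.0 mg. In the first two arms a misplaced day is wrong only about the step. In the 3.0 mg arm it is also wrong about the dose.

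**4. Illustration.** The documents give no distribution of visit days. If Visit 4 were spread evenly over the seven days:
- 6/7 = 85.7% of subjects would be off by at least a day.
- The mean shift would be (3 + 2 + 1 + 0 + 1 + 2 + 3)/7 = 12/7 = 1.7 days.
- Of the first three days at Step 5, (3 + 2 + 1)/(7 × 3) = 6/21 = 28.6% would be counted in Period 1.

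That last share is 0% if every Visit 4 is on Day 22 and 100% if every one is on Day 19. These are subject-days, not events.

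**5. After the change.** With the cut at each subject's actual first Step 5 dose, the misplaced days are 0 in every row.

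**The case against.** The strongest reply is that the SAP already has the better analysis. The summary by actual dose level counts an event at 3 mg on Day 19 under 3 mg, and one at 2 mg on Day 23 under 2 mg. Protocol 9.4.4 adds dose at onset. A reader might infer from the fixed cut that top-dose events are lost, or that the 3.0 mg dose will look better tolerated than it is. The documents do not support that for TEAEs overall.

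A reader might also infer that the SAP equates everything from Day 22 with Step 5. It does not. Only the first period carries a step label, "Period 1 (Day 1 through Day 21; Step 1-4", while the second is simply "Period 2 (Day 22 through end of treatment". By design it includes subjects who went back to the Step 4 dose.

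The effect is also conditional. It needs a Visit 4 away from Day 22 and an onset in the 1 to 3 days between the two dates, or an onset on Day 22 before the clinic dose. The protocol states Day 22 for all subjects and allows no other schedule deviations. If that governs dosing exactly, only the Day 22 pre-dose case remains. The analysis is supplementary and descriptive, and the main adverse event tables in SAP 9.1 do not use this boundary.

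Most of this stands and makes the point small. Three things survive:
- The discontinuation table has no dose-level companion, although SAP 9.1 plans individual listings of those events.
- The dose levels listed do not include placebo, so within SAP 13.1 the period split is what allows a comparison with placebo over the same time.
- The 1 mg level pools Step 3 of both active arms with Steps 4-5 of the 1.0 mg arm, so it does not replace a split by step.

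The no-deviation sentence does not settle the matter either, because the same section has the Step 5 dose taken at a visit that the schedule allows to move.

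**Conclusion.** The point holds as a minor correction. As written, SAP 13.1 can place up to 3 days of Step 5 under a Steps 1-4 heading, or up to 3 days before the first Step 5 dose in Period 2, for any subject whose Visit 4 is not on Day 22. The dose is wrong as well as the step only in the 3.0 mg arm. The dose-level summaries largely cover TEAEs overall, so the weakness is clearest for TEAEs leading to permanent discontinuation. Sample size, power and error rates are unaffected.

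This rests on reading the ±3-day window as applying to Visit 4 in a table flattened by text extraction, and on Step 5 starting at that visit when it moves. How many events would change period cannot be known from the documents.

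**What to change.** In both SAP 13.1 tables, for subjects who take Step 5, end Period 1 immediately before the actual first Step 5 dose and start Period 2 at that dose. All arms follow the same blinded step sequence, so the cut is defined for placebo and the 1.0 mg arm too. The data are collected: "The time and dose of each IMP administration, along with information on any missed or inappropriately administered dose, will be recorded in source documents" and in the eCRF (Protocol 6.4). The final dosing start date used for compliance in SAP 7.2.2 should not be substituted without checking, because for a subject who returned to Step 4 it may not be the first Step 5 dose. State how an event on the day of that dose is assigned when its onset time is missing.

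State also how TEAEs after Day 21 are assigned for subjects who stop before Step 5, since the on-treatment period runs to 28 days after the last dose (SAP 9). One option is to keep them in Period 1, limited to the on-treatment period, and to use subjects who took Step 5 as the Period 2 denominator.

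Separately, the protocol text that fixes Step 5 at Day 22 without other schedule deviations and the ±3-day Visit 4 window should be reconciled.

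The cost is one derived date and a Period 2 denominator that leaves out subjects who never reached Step 5, so that comparison becomes one among those who did. Dropping the step label from Period 1 would be cheaper, but it would correct only the heading and leave the split where it is. Either change should be made before database lock.

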4.4.5. Display of Data Summary and Analysis

Continuous variables will be summarized using descriptive statistics, including the following: sample size (n), mean, standard deviation (SD), median, first quartile (Q1), third quartile (Q3), minimum and maximum for each treatment group.

All mean, Q1, Q3 and median values will be formatted to one more decimal place than the measured value. SD values will be formatted to two more decimal places than the measured value. Minimum and maximum will be formatted to the same number of decimal places as the measured value.

Confidence intervals (CIs) will be two-sided and displayed to the same level of precision as the statistics they relate to. If an estimate or a CI is not estimable, it will be presented as 'NE'. If neither an estimate, nor its CI are estimable, it will be presented as simply 'NE', not displaying 'NE' twice.

The p-values will be two-sided and will be rounded to three decimal places. If a p-value is less than 0.001, it will be reported as '<0.001'. If a p-value is greater than 0.999, it will be reported as '>0.999'.

Categorical and ordinal data will be summarized using the counts and percentages. When count data are presented, the percent will be suppressed when the count is zero in order to draw attention to the non-zero counts. A row denoted 'Missing' will be included in count tabulations

for demographics, baseline characteristics and compliance to account for missing values. No percentages will be displayed on the ‘Missing’ rows and the percentages on the other rows will be based on the number of non-missing observations. Unless otherwise specified, the denominator for all other percentages will be the number of participants in that treatment within the specific analysis set of interest. All percentages will be rounded to one decimal place. The number and percentage of responses will be presented in the form xx (xx.x), where the percentage is in the parentheses. When the numerator is equal to the denominator, the percentage should be presented as (100) instead of (100.0).

All listings will be sorted for presentation in order of assigned treatment arm, study center number, participant number and date of procedure or event.

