7.2. Study Treatments

7.2.1. Extent of Exposure

The extent of IMP exposure will be assessed by the duration of IMP exposure.

Duration of IMP exposure is defined as (last IMP administration dose date – first IMP administration dose date + 1 day), regardless of unplanned intermittent discontinuations. Last IMP administration date is defined as the last available administration date in the “Exposure” form. The reason for early treatment discontinuation will also be based on this last available Exposure form.

Duration of IMP exposure (in weeks) will be summarized descriptively as a quantitative variable (number, mean, SD, median, Q1, Q3, minimum and maximum). In addition, duration of IMP exposure will also be summarized categorically by numbers and percentages for each of the following categories and cumulatively according to these categories:

- >0 and ≤3 weeks
- >3 and ≤6 weeks
- >6 and ≤12 weeks
- >12 weeks

The extent of IMP exposure will be assessed and summarized by actual treatment group and overall for the FAS.

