9. SAFETY ANALYSIS

All randomized subjects who received at least one dose of IMP will be included in the safety analysis. All results will be summarized using the FAS by actual treatment group and CVL-871 Combined, which is defined as combined CVL-871 treatment groups.

The observation periods include:

- The pre-treatment period is defined as the time up to first administration of the IMP.
- The on-treatment period is defined as the time from the first administration of the IMP (on Day 1) to the last administration of the IMP + 28 days.
- The post-treatment period is defined as the time from the last administration of the IMP + 29 days to the end of the study follow-up.

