9.1. Adverse Events

The adverse event (AE) types include:

- **Pre-treatment adverse events** are adverse events that developed up to the first administration of the IMP.
- **Treatment-emergent adverse events (TEAEs)** are adverse events that developed or worsened or became serious during the treatment period.
- **Post-treatment adverse events** are adverse events that developed or worsened or became serious after the treatment period.

The primary focus of adverse event reporting will be on TEAEs. Pre-treatment and post-treatment adverse events will be summarized separately.

All AEs will be coded to a PT and associated primary SOC using the version of MedDRA in effect at the time of database lock.

Adverse events will be recorded from the time of signed informed consent until the end of the study or the resolution/stabilization of all SAE and adverse event of special interest (AESI).

If an adverse event date/time of onset (occurrence, worsening, or becoming serious) is incomplete, an imputation algorithm will be used to classify the adverse event as pre-treatment, treatment-emergent, or post-treatment. The algorithm for imputing date/time of onset will be conservative and will classify an adverse event as treatment-emergent unless there is definitive information to determine it is pre-treatment or post-treatment. Details on classification of adverse events with missing or partial onset dates are provided in [Section 17.2](#).

Adverse events will be summarized by primary SOC and PT, sorted by the internationally agreed SOC order ([MedDRA® Data Retrieval and Presentation: Points to Consider, 2022](#)) and decreasing frequency of PTs in high dose group within SOC unless otherwise specified. In case of equal frequency regarding PTs, alphabetical order will be used. Multiple occurrences of the same event in the same patient will be counted only once in the tables within a treatment phase. The denominator for computation of percentages will be the FAS within each treatment group.

On top of the analysis planned below, all TEAEs, all treatment emergent SAEs, TEAEs leading to permanent treatment discontinuation and TEAEs leading to death will be summarized by treatment group.

Overview summaries of the number and percentages of patients within the following categories will be provided by treatment group and overall for:

- Any TEAE
- Any study drug related TEAE
- Any TEAE of Common Terminology Criteria for Adverse Events (CTCAE) Grade 3 or higher

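### SAP 13.1 gives crude TEAE incidence by dose level without the number exposed or time at each level, and does not place TEAEs that start after the last dose

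*SAP*

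**What the plan says.** SAP 13.1 plans two breakdowns of TEAE incidence. One is by level received: "as well as TEAE incidence by actual dose level (0.25 mg, 0.5 mg, 1 mg, 2 mg, and 3 mg"). The other is by time, with Period 1 covering the first 21 days and the rest defined as "Period 2 (Day 22 through end of treatment"). On columns it says only this: "Summary will also include a total column". It mentions no exposed N, subject-days or placebo entry for the dose levels.

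The denominator comes from the general rules. SAP 9.1: "The denominator for computation of percentages will be the FAS within each treatment group". The default in SAP 4.4.5 works the same way: "the denominator for all other percentages will be the number of participants in that treatment within the specific analysis set of interest". SAP 9 sets the columns for safety output: "All results will be summarized using the FAS by actual treatment group and CVL-871 Combined". It also sets the on-treatment window: "the time from the first administration of the IMP (on Day 1) to the last administration of the IMP + 28 days".

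SAP 7.2.1 summarizes exposure as total duration by arm and overall, with categories that begin at ">0 and ≤3 weeks". SAP 7.2.2 summarizes permitted down-titrations. The by-dose table answers Protocol 9.4.4, which asks for AEs by dose at onset and gives no denominator.

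**The concern.** Safety and tolerability of the two doses is the primary objective, and this is the table a reader would use to judge tolerability step by step. Such a reader will compare percentages across the five levels as if they were dose groups. They are not: each subject passes through several levels, stays at each for a very different time, and reaches the upper levels only if assigned to the 3 mg arm and able to tolerate the earlier steps.

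Without the number exposed and the time at each level, a rising pattern could be taken for dose-relatedness, or a real one could be missed. Time at each level cannot be recovered from the planned summaries, because exposure is not broken down by level.

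**Working it through.** **Inputs.** Days per step are from SAP 3.4, Table 2. Planned size is 25 per arm (SAP 3.1). The TEAE window is from SAP 9 and the 20% discontinuation rate from SAP 4.1. Every hazard below is an assumption.

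**1. Days per step.** End day − start day + 1 gives 3, 4, 9, 5 and 63. The sum is 84 days, or 12 weeks, as in Table 2.

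| Level | Days, 1 mg arm | Days, 3 mg arm | Planned subject-days |
|---|---|---|---|
| 0.25 mg | 3 | 3 | 50 × 3 = 150 |
| 0.5 mg | 4 | 4 | 50 × 4 = 200 |
| 1 mg | 9 + 5 + 63 = 77 | 9 | 25 × 77 + 25 × 9 = 2150 |
| 2 mg | none | 5 | 25 × 5 = 125 |
| 3 mg | none | 63 | 25 × 63 = 1575 |

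The total is 4200 = 50 × 84. Under Protocol 4.1.2, a 3 mg-arm subject who steps back from Step 5 after Day 22 spends 5 + 62 = 67 days at 2 mg instead of 5.

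**2. Constant hazard h, equal at every dose (assumed).** Incidence = 1 − exp(−h × days).

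| h per day | 0.25 mg | 0.5 mg | 1 mg (3 mg arm) | 2 mg | 3 mg | 1 mg (1 mg arm) |
|---|---|---|---|---|---|---|
| 0.002 | 0.6% | 0.8% | 1.8% | 1.0% | 11.8% | 14.3% |
| 0.005 | 1.5% | 2.0% | 4.4% | 2.5% | 27.0% | 32.0% |
| 0.01 | 3.0% | 3.9% | 8.6% | 4.9% | 46.7% | 53.7% |

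There is no dose effect in any row. Pooling also matters. At h = 0.005, a 1 mg column holding both arms reads (32.0 + 4.4)/2 = 18.2%. The 3 mg level reads 27.0% on the 25 exposed, but 27.0/2 = 13.5% on all 50 active subjects, so the denominator alone reverses the order of 1 and 3 mg.

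**3. Events clustered at dose increases (assumed 0.03/day for the first 3 days at a level, then 0.003/day).** Cumulative hazard = 0.09 + 0.003 × (days − 3). In the 3 mg arm, the five levels read 8.6, 8.9, 10.2, 9.2 and 23.7%. The four lower levels are nearly flat. Cumulative hazard divided by days, per 100 subject-days, is 3.0, 2.3, 1.2, 1.9 and 0.4, so the rates fall with dose although the hazard pattern is the same at every level. If events occur only just after each step, at 10% per step, every level reads 10% whatever its length.

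**4. Combined and total columns.** With equal arms, dividing 2 or 3 mg events by the FAS N of two arms multiplies the arm figure by 1/2 = 0.50; dividing by three arms multiplies it by 1/3 = 0.33. For 10 subjects with an event: 10/25 = 40%, 10/50 = 20%, 10/75 = 13.3%. This arises only if FAS N is used in those columns.

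**5. Period 2.** The FAS percentage equals the at-risk percentage × (1 − fraction leaving before Day 22): 1.00, 0.95, 0.90 or 0.80 if 0, 5, 10 or 20% leave. The documents do not give the timing; 0.80 puts the whole planned 20% early. The factor is exact only if post-dose events stay out of Period 2. The number dosed on Day 22 or later can be recovered: 3 weeks is 21 days, so it is FAS N minus the first exposure category.

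**6. After the last dose.** A completer has 84 + 28 = 112 TEAE days, of which 28 (25%) follow the last dose. A subject who stops on Day 10 has a window to Day 38, so 38 − 22 + 1 = 17 TEAE days fall after Period 1. If post-dose events go to the last level, a subject who stops on Day 3 has 3 + 28 = 31 days at 0.25 mg.

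**The case against.** The strongest reply is that no constant hazard is documented and the documents lean the other way. Titration exists to mitigate nausea and vomiting (SAP 3.4), nausea was the most frequent AE in both prior trials (Protocol 2.2.4), and tolerability is checked at dose increases (Protocol 4.1.2). This stands. A reader might infer that the level percentages will mostly reflect time at risk; the documents do not support that, because it needs an assumed hazard.

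A reader might also infer that the 2 and 3 mg percentages will be halved or cut to a third. That depends on a layout SAP 13.1 does not specify. The table shells are a separate document (SAP 1), not available here, and may already fix the columns and Ns.

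Nor is the FAS percentage for Period 2 an error. It keeps the comparison between arms as randomized, scheduled period length is the same in every arm, and the at-risk N is recoverable.

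It would also be too strong to say that no rule covers events after the last dose. SAP 9 makes them treatment-emergent for 28 days, and the end of Period 2 could be read as the end of that window. What is unstated is their dose level, and whether Period 2 takes them.

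Finally, exposure-adjusted rates are not a cure. In the clustering case they run from 3.0 down to 0.4, a larger spurious contrast than the crude 8.6% to 23.7%, and in the opposite direction.

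None of this supplies the number exposed at a level, the time spent there, or a placebo reference for the same steps.

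**Conclusion.** The point holds as a cheap improvement. The stated denominator does not match a dose level, planned time differs up to 21-fold between levels in the 3 mg arm (63/3), and the levels draw on different arms with no placebo entry. Percentages across levels can therefore differ for reasons other than dose. Under an assumed constant hazard the effect is large (0.6% against 11.8% at 0.002/day, and 3.0% against 46.7% at 0.01/day, for 0.25 and 3 mg). Under assumed clustering it is small among the four lower levels of the 3 mg arm. The day counts are from the schedule; the hazards are not in the documents, and full adherence is assumed.

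The allocation of TEAEs that start after the last dose to a level or period is unstated. The table is supplementary and descriptive, and early closure of enrollment will make its cells small. The main by-arm TEAE tables are unaffected.

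**What to change.** In SAP 13.1:

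- Keep the FAS counts and percentages by arm.
- Show dose levels within treatment arm, with placebo for the same titration steps.
- Beside them print the number of subjects with at least 1 dose at that level or in that period, percentages on that N, and subject-days. Note that this group is selected by tolerability and is not a randomized comparison.
- Do not divide 2 and 3 mg events by arms that never receive those levels; leave those Combined and total cells blank or use the exposed N.
- List TEAEs that start after the last dose in a separate row, or assign them to the last level and period and count subject-days by the same rule.
- Add exposure-adjusted rates only beside the crude percentages, with a note that they dilute events clustered at dose increases.

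If the shells already do this, state the rules in SAP 13.1.

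The cost is SAP wording and modest programming, since Protocol 6.4 already has the time and dose of each administration recorded in the eCRF. The downsides are busier supplementary tables, small cells, and conditional percentages that must not replace the FAS ones for comparing arms.
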